5. STATISTICAL METHODOLOGY

5.1. GENERAL METHODOLOGY

Analysis will be performed when all subjects enrolled have been followed for survival for two years (24 months) from the date of their first TACE, are considered lost to follow up, or have died, whichever comes first.

For continuous variables, outputs will be presented with mean, standard deviation (SD), median, minimum, and maximum values. Mean and median will be rounded to a single decimal while SD will be rounded to two decimals. When appropriate, a corresponding 95% confidence interval (CI) will be calculated. Categorical variables (e.g., sex and race) will be reported using frequencies and percentages. All percentages will be rounded to single decimal. If percentages do not add up to 100% due to rounding, a footnote mention will be provided accordingly.

Correlation analyses will be used to analyze relationships for continuous variables. Fisher's exact test will be used to analyze relationships between categorical variables. P-values less than or equal to 0.05 will be considered significant. All p-values will be rounded to 3 decimal places and will be presented as "<0.001" if less than 0.0005.

Survival analyses will be performed using Kaplan-Meier with corresponding median survival times and 95% CIs.

Descriptive statistics will be used to examine demographic and baseline characteristics and to perform other efficacy analyses.

Each table generated will have headers that include the total sample size (N). Frequencies and percentages for categorical variables will be calculated using the number of subjects (n) with non-missing values.

DATA SOURCE

All data will be extracted from Medidata. Datasets will be merged and cleaned prior to data analysis. Data processing procedures will be documented to ensure replicability and error checking.

REPORTING OUTPUTS

SAS 9.4® and SPSS 27.0® will be used to produce all statistical analysis and figure outputs. Tables will be formatted through Microsoft® Word.

HANDLING OF MISSING DATA

There will be no imputation of missing data as the study is observational and all analyses performed should not require such methods.

SITE POOLING

To assess the consistency of observed treatment effect across investigational sites, a data poolability analysis will be performed on the primary efficacy outcomes of overall survival. Median overall survival data will be summarized by site, including Kaplan-Meier plots.

CLASSIFICATION OF PROTOCOL VIOLATION

Protocol deviations will be summarized in the final clinical study report. Essential clinical documents will be maintained to demonstrate the validity of the study and the integrity of the data collected.

5.2. PRIMARY DATA ANALYSES

Median overall survival times will be calculated using the Kaplan-Meier (product-limit) method and corresponding 95% confidence intervals will be generated. One- and two-year survival rates and corresponding 95% confidence intervals will also be calculated.

5.3. SECONDARY DATA ANALYSES

Objective Response Rate

Descriptive statistics will be used to analyze and summarize ORR. Ninety-five percent confidence intervals will be calculated.

Best Tumor Response

Best tumor response will be summarized as the number and percentage of patients in each response category (CR, PR, SD, PD) for the effectiveness population using descriptive statistics.

Median Liver progression-free survival

Median liver PFS will be calculated using Kaplan-Meier (product-limit) and corresponding 95% confidence intervals will be generated.

Time to Progression

TTP will be summarized using descriptive statistics and corresponding 95% confidence intervals will be generated.

Safety Summary

Safety summaries will be summarized using descriptive statistics and will include information regarding AEs, serious adverse events (SAEs), and TACE-related AEs.

5.4. EXPLORATORY DATA ANALYSES

Pharmacokinetic (PK) Analyses

Data will be summarized by descriptive statistics, including mean, standard deviation, coefficient of variation, minimum, maximum, and median. The correlation between circulating levels of irinotecan and SN38 and overall survival, tumor response, and treatment-related adverse events will be evaluated to the extent possible with the available PK data. A Pearson's correlation or a Spearman's rank correlation will be performed depending on whether the variable being compared to levels of irinotecan and SN38 is continuous or categorical.

Additional TACE Cycles

Kaplan-Meier estimator with log-rank testing will be used to compare overall survival of standard TACE cycles to additional TACE cycles. Comparison of additional TACE cycles between tumor response will be performed using Fisher's exact test.

RECIST 1.1

The best tumor response will be compared between mRECIST and RECIST 1.1 using Fisher's exact test.

Clinical Success

Clinical success will be summarized using descriptive statistics.

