2. BACKGROUND/INTRODUCTION

2.1. STUDY DESIGN

This prospective, single arm, post-market clinical trial is designed to demonstrate safety and efficacy of Merit Medical Systems' HepaSphere Microspheres loaded with irinotecan for subjects with metastatic colorectal cancer to the liver. There will be two hospitals participating in this study, one in Greece (N=100) and one in France (N=5). Hospitals and physicians with experience in routine use of chemoembolization for metastatic colorectal cancer (mCRC) to the liver will participate. Subject recruitment and offer to participate in the study will be at the investigator's discretion (ensuring that subjects are existing patients receiving care at the hospital and that they meet inclusion and exclusion criteria). All enrolled and treated subjects will be followed for survival until data analysis. Data analysis will be performed when all treated subjects actively being followed for survival have individually cumulated a minimum of two years (24 months) since the date of their first study TACE procedure.

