4. OUTCOME VARIABLES

4.1. PRIMARY OUTCOME

Patient survival will be calculated in months from the date of the first TACE procedure until a date of death is obtained or the subject is lost to follow up (utilizing the last successful contact with the patient). Median overall survival time will be the primary outcome of the study.

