Outcomes	mRECIST (N =83) n (%)	RECIST 1.1 (N = 78) n (%)	p-value
Best Tumor Response	0.xxx		
CR	xx (xx.x)	xx (xx.x)	
PR	xx (xx.x)	xx (xx.x)	
SD	xx (xx.x)	xx (xx.x)	
PD	xx (xx.x)	xx (xx.x)	

Note: Percentages may not add up exactly due to rounding

Table 7. Additional TACE Cycles

Outcomes	Standard TACE Cycles (N=76)	Additional TACE Cycles (N=29)	Log rank test	Fisher's exact test
Median Overall Survival (in months)	xx.x	xx.x	p = 0.xxx	
Best Tumor Response: n (%)				p = 0.xxx
CR	xx (xx.x)	xx (xx.x)		
PR	xx (xx.x)	xx (xx.x)		
SD	xx (xx.x)	xx (xx.x)		
PD	xx (xx.x)	xx (xx.x)		
Not Assessed	xx (xx.x)	xx (xx.x)		

Note: Percentages may not add up exactly due to rounding

Table 8. PK Analyses

Variables	N	Mean	SD	Median	Min	Max	R (p-value)
Irinotecan (ng/ML): 30 minutes	xx	xxx.x	xxx.xx	xxx	xxx	xxx	
with Overall Survival							x.x (0.xxx)
with Tumor Response							x.x (0.xxx)
with Treatment-Related AEs							x.x (0.xxx)
Irinotecan (ng/ML): 1 hour	xx	xxx.x	xxx.xx	xxx	xxx	xxx	
with Overall Survival							x.x (0.xxx)
with Tumor Response							x.x (0.xxx)
with Treatment-Related AEs							x.x (0.xxx)
Irinotecan (ng/ML): 4 hours	xx	xxx.x	xxx.xx	xxx	xxx	xxx	
with Overall Survival							x.x (0.xxx)
with Tumor Response							x.x (0.xxx)
with Treatment-Related AEs							x.x (0.xxx)
Irinotecan (ng/ML): 24 hours	xx	xxx.x	xxx.xx	xxx	xxx	xxx	
with Overall Survival							x.x (0.xxx)
with Tumor Response							x.x (0.xxx)
with Treatment-Related AEs							x.x (0.xxx)
SN38 (ng/ML): 30 minutes	xx	xxx.x	xxx.xx	xxx	xxx	xxx	
with Overall Survival							x.x (0.xxx)
with Tumor Response							x.x (0.xxx)
with Treatment-Related AEs							x.x (0.xxx)
SN38 (ng/ML): 1 hour	xx	xxx.x	xxx.xx	xxx	xxx	xxx	
with Overall Survival							x.x (0.xxx)
with Tumor Response							x.x (0.xxx)
with Treatment-Related AEs							x.x (0.xxx)
SN38 (ng/ML): 4 hours	xx	xxx.x	xxx.xx	xxx	xxx	xxx	
with Overall Survival							x.x (0.xxx)
with Tumor Response							x.x (0.xxx)
with Treatment-Related AEs							x.x (0.xxx)
SN38 (ng/ML): 24 hours	xx	xxx.x	xxx.xx	xxx	xxx	xxx	
with Overall Survival							x.x (0.xxx)
with Tumor Response							x.x (0.xxx)
with Treatment-Related AEs							x.x (0.xxx)

[figure not shown]
[figure not shown]
[figure not shown]
[figure not shown]
Figure 1. Kaplan-Meier survival curve for overall survival**Figure 2. Kaplan-Meier survival curve for progression free survival**

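### The PK analysis relates drug levels to overall survival by a correlation coefficient that takes no account of censoring

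*SAP*

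**What the plan says.** SAP 5.4 (Pharmacokinetic Analyses) will evaluate "The correlation between circulating levels of irinotecan and SN38 and overall survival", along with tumor response and treatment-related adverse events, as far as the PK data allow. The choice of coefficient rests only on variable type, with one class for continuous and one for categorical variables: "A Pearson's correlation or a Spearman's rank correlation will be performed depending on whether the variable being compared to levels of irinotecan and SN38" falls in the one class or the other. SAP 5.1 has the same general rule, "Correlation analyses will be used to analyze relationships for continuous variables", with no exception for censored times.

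Table 8 in SAP 6.2 has a row "with Overall Survival", filled by R and a p-value, at 30 minutes, 1, 4 and 24 hours for irinotecan and again for SN38. That is 2 x 4 = 8 survival correlations. SAP 5.1 calls p-values of 0.05 or less significant.

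SAP 4.1 measures survival from the first TACE "until a date of death is obtained or the subject is lost to follow up", using the last successful contact in the latter case. SAP 2.1 and 5.1 trigger the analysis once patients still being followed have reached at least 24 months. Elsewhere the SAP treats survival as censored: "Survival analyses will be performed using Kaplan-Meier with corresponding median survival times and 95% CIs" (SAP 5.1), Kaplan-Meier for the primary outcome (SAP 5.2), and Kaplan-Meier with a log-rank test for additional TACE cycles (SAP 5.4).

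**The concern.** A patient alive at analysis, or lost, contributes a lower bound on survival and not a survival time. Kaplan-Meier and log-rank use that information correctly; Pearson and Spearman have no place for an event indicator. To compute Table 8, the analyst must either enter follow-up time as if it were survival time or leave out everyone without a death date. The SAP chooses neither, and its statement that missing data will not be imputed does not settle the matter.

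At stake is the reading of the exposure-survival result. In a small PK subset, a weakened R may be taken as evidence that circulating drug level does not matter. An R computed on a mixture of death times and follow-up times also has no clear clinical meaning.

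**Working it through.** The plan gives no figure to reproduce: there is no PK sample size, expected correlation or power. The check asks how much censoring to expect and what it does to the planned coefficient.

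**1. Expected censoring at 24 months.** With exponential survival and median m, the share alive is 0.5^(24/m).
- m = 19 months (55-patient cohort cited in Protocol 1.0): 0.5^(24/19) = 0.42.
- m = 24 months (82-patient cohort cited in Protocol 1.0): 0.5^(24/24) = 0.50.
- TACE arm of the cited phase III trial: 56% alive at two years, as reported.

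So roughly 42-56% would be censored if follow-up ended at 24 months. SAP 2.1 follows patients until data analysis, so follow-up may be longer. Under an assumed uniform 24-60 months, about 32% remain censored at a median of 24 months with the effect size used in step 3.

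**2. Effect on the coefficient (large-sample simulation).** Assumptions: normally distributed standardized drug level; exponential survival with hazard ratio (HR) 1.5 per SD; median 14.1, 19 or 24 months (14.1 is a cited mean survival, used only as a low value); follow-up capped at 24 months or uniform over 24-60; 0-20% lost by 24 months.

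| HR 1.5 per SD | True survival times | Follow-up used as survival | Deaths only |
|---|---|---|---|
| Pearson | about -0.35 | -0.22 to -0.32 | -0.09 to -0.22 |
| Spearman | about -0.32 | -0.22 to -0.31 | -0.09 to -0.21 |

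Example for Pearson (median 19, 24-month cap, 10% lost): true -0.349, follow-up as survival -0.254, deaths only -0.112. The shrinkage is 1 - 0.254/0.349 = 27% and 1 - 0.112/0.349 = 68%. Over all settings at this HR, using follow-up time makes Pearson about 7-38% too small. At HR 2.0 the shortfall is at most 25%, and in one setting (median 14.1, 24-60 months, no loss) the coefficient is slightly too large: -0.484 against -0.462.

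**3. Power (two-sided 0.05).** Assumptions: median 24 months, HR 1.8 per SD of log concentration, log-scale SD about 0.5, no loss to follow-up. Pearson uses raw concentration and follow-up time; Cox uses log concentration.

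| PK patients | Follow-up | Censored | Pearson | Cox |
|---|---|---|---|---|
| 40 | 24-month cap | 49% | 0.63 | 0.70 |
| 40 | 24-60 months | 32% | 0.72 | 0.81 |
| 20 | 24-month cap | 49% | 0.36 | 0.40 |
| 20 | 24-60 months | 32% | 0.38 | 0.49 |

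**4. Type I error.** With no true association and censoring unrelated to drug level, Pearson and Spearman reject in 4.7-5.2% of trials at n = 15, 30 and 60. If follow-up runs over 24-60 months and its length is correlated with drug level, Pearson at n = 40 rejects in about 7% at a correlation of 0.2-0.3 and 13% at 0.6. Separately, if loss to follow-up depends on drug level (HR for loss 1.5-2 per SD, 10-20% lost, 24-month cap), a spurious correlation of -0.03 to -0.12 appears.

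**The case against.** The strongest reply is that little depends on this analysis. Protocol 2.3 makes it conditional on sufficient data, Protocol 7.3 and SAP 5.4 limit it to what the PK data allow, and only an unstated portion of patients is sampled. No primary, secondary or safety result uses it. That stands and sets the severity, but it bears on the amount of data and not on the choice of method.

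Four stronger readings are tempting and should be resisted.

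- *The correlations will produce false positives.* They keep their size unless censoring is related to drug level, and nothing in the documents suggests that it is. The enrolment-date route also needs follow-up beyond 24 months. Footnote 4 of the Schedule of Procedures describes survival follow-up for two years after the first TACE; if contacts stop there, follow-up of living patients is equal and that route closes.
- *The SAP states that censored times count as deaths.* It does not. This follows from the definition in SAP 4.1 and the lack of any other rule. The alternative, deaths only, attenuates more.
- *The power gap in step 3 is the cost of censoring.* It is not purely that. The comparison also changes the concentration scale: with a log-scale SD of 1.0 and n = 40, Pearson on raw concentration has power 0.50 even with no censoring. The Cox score test is also slightly oversized in small samples (0.056-0.059 at n = 15-30).
- *Log-rank is used for every other survival analysis.* It is planned only for additional TACE cycles; the site comparison uses medians and plots.

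**Conclusion.** The point holds in a limited form. As written, the SAP leads to Pearson coefficients between drug level and a right-censored time, with no rule for patients without a death date. The usual effect is to attenuate a true association: about 7-38% for Pearson at HR 1.5 per SD if follow-up time is used, and more with deaths only. Moving to Cox raises power in the illustration by 0.04 to 0.11 (0.40 - 0.36 to 0.49 - 0.38), which is best read as the gain from the whole change of method.

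These sizes rest on exponential survival, medians borrowed from the cited studies, and PK sample and effect sizes that the documents do not give. The problem would vanish only if every PK patient had died by the analysis. The documents do not support a claim of generally inflated false positives, and the primary survival result is untouched. Severity: a change to consider.

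**What to change.** In SAP 5.4 and the survival rows of Table 8, replace the correlation with a Cox model of overall survival on log concentration for each analyte and time point. State that patients alive or lost are censored at last contact. Report the hazard ratio per doubling of concentration with its 95% confidence interval, and label the rows exploratory. Add to the general correlation rule in SAP 5.1 that it does not apply to time-to-event outcomes. Protocol 7.3 names no coefficient, so the model can be specified in the SAP.

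The tumor response and adverse event rows need no change on this account, since they are not censored times.

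The cost is a few lines of text and a revised set of rows in Table 8. The dates are already collected, and the SAS version named in SAP 5.1 can fit the model.

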2.3 Additional Analyses

If sufficient data is available, additional exploratory analyses will also be conducted. These may include, but are not limited to:

- Pharmacokinetic (PK) Analyses: Plasma concentrations of irinotecan and SN38 will be analyzed at the following timepoints after the first TACE procedure: 30 minutes, 1 hour, 4 hours, 12 hours, and 24 hours or prior to discharge (whichever comes first).
- Additional TACE Cycles: The relationship between 'Additional TACE cycles,' (defined as cycles a subject may undergo after the protocol specified TACE 1 and TACE 2) and overall survival time (in months)
- RECIST 1.1: Reanalyze clinical outcomes using RECIST 1.1 criteria and compare best tumor response between RECIST 1.1 and mRECIST criteria.
- Clinical Success: Similar to ORR, clinical success will be based on the last post TACE liver response evaluated through mRECIST and RECIST 1.1 criteria. Clinical success is the total amount of confirmed subjects that have a complete or partial response [clinical success = (# CR + #PR)]

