7.3 Additional Analyses

Pharmacokinetic (PK) Analyses

PK blood samples drawn from a portion of the subjects after the first TACE cycle (at four pre-determined time periods) will undergo bioanalytical analysis using validated assays. The assays will measure the subject's plasma concentrations of irinotecan and its active metabolite, SN38. Data will be summarized by descriptive statistics, including mean, standard deviation, coefficient of variation, minimum, maximum, and median. The correlation between circulating levels of irinotecan and SN38 and overall survival, tumor response, and treatment-related adverse events will be evaluated to the extent possible with the available PK data.

Additional TACE Cycles

Overall survival time will be compared between standard TACE cycles and additional TACE cycles (any TACE procedure(s) beyond the protocol specified TACEs) using Kaplan-Meier estimator with log-rank testing. Comparison of additional TACE cycles between tumor response will be performed using Fisher's exact test.

RECIST 1.1

Clinical outcomes will be reanalyzed based on RECIST 1.1 criteria. The best tumor response will be compared between mRECIST and RECIST 1.1 using Fisher's exact test.

Clinical Success

Similar to ORR, clinical success will be based on the last post TACE liver response evaluated through mRECIST and RECIST 1.1 criteria. Clinical success is defined as the total number of confirmed subjects who exhibit a complete or partial response [clinical success = (# CR + #PR)].

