2.6. STUDY PROCEDURE

Study subjects (once screened, enrolled, and consented) must undergo a complete baseline evaluation. The evaluation includes haematology and serum chemistry assessments and imaging (CT or contrast-enhanced MRI of the liver).

Subjects must have two TACE cycles. A TACE cycle is defined as one embolization for patients with unilobar disease or two embolizations for subjects with bilobar disease (one for each lobe of the liver). The second TACE cycle should be performed within 2-4 weeks after the first TACE cycle. Subsequent TACE cycles may be performed for residual or new disease as needed (at the investigators discretion), based on tumor response. See 'Schedule of Procedures' below for additional information.

Schedule of Procedures

	Screening ¹	TACE Procedure ²	Follow Up Visits ³	Survival Follow-up ⁴
Informed Consent	X			
Eligibility criteria assessment	X			
Demographics	X			
Medical History	X			
Tumor Evaluation / Imaging	X		X	
Hematology / Serum Chemistry	X			
Embolization procedures (TACE)		X		
Pharmacokinetic Sampling ⁵		X		
Additional cancer treatments			X	
Adverse Events		X	X	
Survival status				X

¹ Screening imaging must be within 4 weeks of first TACE cycle.

² First TACE cycle must be within 4 weeks of screening imaging. If the patient has bilobar disease, the embolization of the first lobe must be within 4 weeks of screening imaging and the second lobe must undergo embolization within 3 weeks (\pm 2 weeks) of the first lobe. A second TACE cycle is required for all patients 2-4 weeks after the first TACE cycle. Additional TACE cycles can be performed for residual or new disease as needed.

³ Follow up Visits will start 4-6 weeks after the second TACE cycle and occur every 12 weeks (\pm 2 weeks) thereafter during the first year of follow-up. Follow-up may be more frequent if medically indicated.

⁴ If patients are no longer indicated for TACE, they will continue to be followed for survival for 2 years after the first TACE procedure, with contacts performed every 3 months (\pm 2 weeks).

⁵ Blood samples will be drawn for PK analysis from a portion of study patients after the first TACE procedure at the following time points; 30 min, 1 hour, 4 hours, 12 hours, and 24 hours or prior to discharge (whichever comes first).

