4.3. OTHER PARAMETERS

Pharmacokinetic (PK) Analyses

PK blood samples drawn from a portion of the subjects after the first TACE cycle (at four pre-determined time periods) will undergo bioanalytical analysis using validated assays. The assays will measure the subject's plasma concentrations of irinotecan and its active metabolite, SN38.

Additional TACE Cycles

Overall survival time will be compared between standard TACE cycles and additional TACE cycles (any TACE procedure(s) beyond the protocol specified number of TACE cycles).

RECIST 1.1

Clinical outcomes will be re-analyzed based on RECIST 1.1 criteria. The best tumor response will be compared between mRECIST and RECIST 1.1.

Clinical Success

Similar to ORR, clinical success will be based on the last post-TACE liver response evaluated through mRECIST and RECIST 1.1 criteria. Clinical success is defined as the total number of confirmed subjects who exhibit a CR or PR [clinical success = (# CR + #PR)].

Demography and Baseline

Subject demographic information and other baseline data will be included and summarized. Sex, age, race, and ethnicity will be included as demographic characteristics. Medical history will be described through system organ class (SOC) and baseline risk factors. Subject hepatic health status such as prior hepatic treatment and tumor location will also be provided.

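### The exploratory survival comparison of standard and additional TACE cycles makes no allowance for the time a patient must survive to receive a third cycle

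*SAP*

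**What the plan says.** The comparison is in SAP 5.4: "Kaplan-Meier estimator with log-rank testing will be used to compare overall survival of standard TACE cycles to additional TACE cycles". Protocol 7.3 has the same plan: "Overall survival time will be compared between standard TACE cycles and additional TACE cycles".

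The groups are defined by what happens after the start of treatment. Protocol 2.3 describes additional cycles as "cycles a subject may undergo after the protocol specified TACE 1 and TACE 2", and SAP 4.3 as "any TACE procedure(s) beyond the protocol specified number of TACE cycles". SAP 2.6 says how they arise: "Subsequent TACE cycles may be performed for residual or new disease as needed (at the investigators discretion), based on tumor response". Protocol 5.3 adds that the liver should still be the dominant metastatic site and liver enzymes should be acceptable.

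The survival clock starts earlier. SAP 4.1: "Patient survival will be calculated in months from the date of the first TACE procedure".

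The Table 7 shell in SAP 6.2 gives 76 standard and 29 additional patients, a log-rank p-value, a Fisher p-value for best tumor response and a row for patients not assessed. SAP 6.1 lists a matching Kaplan-Meier plot as Figure 4. SAP 5.1 sets the rule: "P-values less than or equal to 0.05 will be considered significant". Neither document mentions a landmark, a time-dependent covariate, a later time origin or a caution on interpretation.

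**The concern.** A log-rank test assumes that group membership is known at time zero. Here it is not. A patient who dies before a third cycle could be given is counted as standard whatever the physician would have done, and a patient in the additional group cannot die between the first TACE and the third cycle. That guaranteed (immortal) time is credited to the additional group.

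At stake is one exploratory result. With its own p-value, figure and significance rule, it could be reported as an association between further cycles and longer survival when the grouping alone produced the difference.

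The Fisher comparison has a related, secondary weakness. Cycles are chosen in the light of tumor response, and under SAP 4.2 best response runs to the last scan, so it can include scans taken after the extra cycles. Response is partly the cause of the grouping and partly measured after it.

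**Working it through.** The plan states no power, event count or effect size for this comparison, so there is no design figure to reproduce.

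**Who is compared.** 76 + 29 = 105. This equals the site totals in SAP 2.1 (100 + 5 = 105) and the N in the Table 3 safety shell. It exceeds the 83 mRECIST patients in Tables 5 and 6 by 105 - 83 = 22. SAP 3.1 requires a post-baseline tumor evaluation for efficacy analyses, but Table 7 appears to use everyone treated. SAP 2.3 admits patients after one procedure, so a patient who died before cycle 2 would count as standard.

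**When a third cycle can occur.** Cycle 2 follows cycle 1 by 2-4 weeks, and SAP 2.6 says "Follow up Visits will start 4-6 weeks after the second TACE cycle", that is 4-6 weeks later. A response-based third cycle at the first visit therefore comes 2 + 4 = 6 to 4 + 6 = 10 weeks after first TACE (later with staged bilobar treatment). Three more 12-weekly visits from the midpoint reach 8 + 36 = 44 weeks.

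**Deaths by then.** With exponential survival and median m months, the proportion dead by t months is 1 - 2^(-t/m). Medians of 7 and 21 months come from protocol 1.0 (26-50% and under 25% liver involvement in a 29-patient series with this product); 12 is an interpolation. Weeks are converted as weeks × 7 / 30.4375.

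| Time from first TACE | m = 7 | m = 12 | m = 21 |
|---|---|---|---|
| 6 weeks (1.38 months) | 12.8% | 7.7% | 4.5% |
| 10 weeks (2.30 months) | 20.4% | 12.4% | 7.3% |
| 3 months | 25.7% | 15.9% | 9.4% |
| 44 weeks (10.12 months) | 63.3% | 44.3% | 28.4% |

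These patients can only be standard unless they had a third cycle first.

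**Effect on the test.** Null simulation: a third cycle has no effect, patients are selected at random, N = 105, about 29 additional, medians 7-21 months, follow-up 24 or an assumed 48 months, two-sided 0.05 (the SAP does not state sidedness). The hazard ratio (HR) is additional versus standard; its ranges in the table are approximate, and all but the first-visit figure in the right-hand column also cover a 24-month median.

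| Timing of third cycles | Exponential survival | No deaths before 3 months |
|---|---|---|
| All at first visit | 6-20%, HR 0.77-0.91 | about 5%, HR 1.00-1.01 |
| Spread to about 44 weeks | 19-81%, HR 0.53-0.76 | 9-46%, HR 0.68-0.85 |

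The right-hand column takes the inclusion criterion of life expectancy of at least 3 months as a guarantee. First-visit bias then vanishes, because 10 weeks (2.30 months) falls before any death. Under exponential survival, a test with the third cycle as a time-dependent covariate rejected in 4-6% of trials (HR 0.99-1.01), and a 6-month landmark in 4.3-6.0% (HR 0.98-1.02).

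**Selection.** Assume a latent HR of 2 in half the patients and a selection odds ratio of 3, with exponential survival. In all 105, the HR from the planned analysis is then 0.88-1.07 (first visit) or 0.61-0.89 (spread) if worse-prognosis patients get third cycles, and 0.65-0.75 or 0.44-0.62 if better-prognosis patients do. In an 83-patient stand-in for the SAP 3.1 set, worse-prognosis selection at the first visit gives 1.20-1.22, against additional cycles.

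**The case against.** The strongest case against concerns size and weight. The life-expectancy criterion should thin out the early deaths that drive the bias, and in the limiting case it removes the first-visit bias. It is a prognosis and not a guarantee, so it bounds the answer; it does not remove the bias when cycles are spread. The upper figures use a 7-month median from a subgroup with 26-50% involvement, while this trial admits everyone up to 50%. That stands: they are extreme. Restricting to patients with a scan would also help. In the 83-patient stand-in with random selection, first-visit timing gives 5-6% false positives, but spread timing still gives 9-42%.

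The analysis is also exploratory, conditional on sufficient data (protocol 2.3), and part of a study that disclaims comparisons between cohorts in its sample-size section. A corrected model remains confounded by selection: under the assumptions above its HR is still 1.20-1.23 or 0.81-0.86. This stands too, and is why any estimate should be descriptive.

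A reader might infer that the planned test must favour additional cycles, or that a false positive is likely. The documents support neither: they give no third-cycle dates, and selection can offset or reverse the immortal-time component. Nor does the point reach the primary endpoint, where all patients are counted from first TACE without grouping.

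**Conclusion.** The flaw is certain in structure and uncertain in size. As written, the plan fixes groups by a later event and tests them from first TACE, so its p-value has no reliable meaning. Without selection the distortion ranges from none (all third cycles at the first visit, no deaths before 3 months) to a false-positive rate of about 81% (cycles spread, exponential survival, 7-month median). These figures rest on assumed survival shape, medians, third-cycle timing and random selection; only the group sizes, visit windows and 24-month minimum follow-up come from the plan. The net direction in the real data cannot be predicted. It should be corrected, at low priority, because it concerns one exploratory comparison.

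**What to change.** Remove the fixed-group log-rank p-value from SAP 5.4 and Table 7.

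- If the dates of first additional cycles are in the database, use a Cox or Mantel-Byar analysis with the first additional cycle as a time-dependent covariate, or a landmark analysis with the landmark set in advance. Replace Figure 4 with a matching plot (Simon-Makuch or landmark). Report the HR and 95% CI as descriptive, stating that selection remains.
- If the dates are not available, show the two groups descriptively, with no p-value and a sentence on immortal time.
- State whether Table 7 uses all 105 treated patients or the SAP 3.1 efficacy set.
- Report tumor response by additional cycles descriptively, without the Fisher p-value.

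The cost is SAP wording, one short program and one figure; the descriptive option needs no new program. The documents do not say that later-cycle dates are captured, so confirm this first. Precision will be low. Around an HR of 1, the 95% CI would run from about 0.5-0.6 to 1.6-2.0 for the time-dependent model, and from 0.4-0.6 to 1.7-2.4 for a 6-month landmark. Under the exponential assumptions, that landmark keeps 58-88 of 105 patients, with about 15-16 additional if cycles are spread and 19-26 if all come at the first visit.
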